6.2 Exclusion Criteria

- 1) Prior minor papilla therapy (endoscopic or surgical)
- 2) Calcific chronic pancreatitis, defined as parenchymal or ductal calcifications identified on computed tomography or magnetic resonance imaging scan that is reviewed by an expert radiologist at the recruiting site.
- 3) Main pancreatic duct stricture*
- 4) Presence of a structural etiology for acute pancreatitis, such as anomalous pancreaticobiliary union, periamppullary mass, or pancreatic mass lesion on imaging*
- 5) Presence of a local complication from acute pancreatitis which requires pancreatogram
- 6) Regular use of opioid medication for abdominal pain for the past three months
- 7) Medication as the etiology for acute pancreatitis by physician assessment
- 8) TWEAK score ≥ 4
- 9) Hypertriglyceridemia, defined as a serum triglyceride level $> 500\text{mg/dL}$ during a prior episode of acute pancreatitis
- 10) Hypercalcemia, defined as a corrected serum calcium level $> 10.5\text{mg/dL}$ associated with a prior episode of acute pancreatitis
- 11) Clinical presentation consistent with type I or type II autoimmune pancreatitis
- 12) Pregnancy (urine test)
- 13) Low probability of follow-up on a regular basis to achieve study objectives
- 14) Life expectancy < 6 months based on the opinion of the physician investigator

15) Incarceration

*The possible presence of a pancreatic duct stricture or structural etiology for acute pancreatitis will be assessed for all subjects during review of the MRCP. If no evidence of either exclusion is identified during review of MRCP, and all other eligibility criteria are met, subjects who consent to randomization will be scheduled for the pre-randomization EUS. Absence of pancreatic duct stricture and structural etiology will be confirmed during EUS before a subject can be randomized.

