8.2 Eligibility Assessment

Any patient ≥ 18 years old who is believed to have iRAP and suspected pancreas divisum will be considered for inclusion in the study. Prior to approaching a potential subject regarding study participation, study staff may review the existing available medical

records for evidence of exclusion criteria. If no evidence of exclusion criteria is identified, the patient will be approached to discuss study participation.

As in all trials, the goal is to achieve a high level of compliance with protocol requirements by assuring, during the eligibility assessment, that the potential participant is fully informed and agrees to the protocol requirements. In addition, participants with a strong likelihood of non-adherence (e.g. for reasons such as difficulties in adhering to follow-up schedule) should not knowingly be enrolled. Adherence of the clinical center staff to careful assessment of the participant's understanding of the trial and a clinical center environment which supports the continued commitment of the participants are essential for the trial to be successfully completed.

Conditional Eligibility: Once a subject has agreed to study participation and informed consent has been obtained and documented, research personnel begin screening procedures required to determine conditional eligibility. Full eligibility for this trial cannot be assessed until EUS is performed immediately prior to randomization.

The following will be performed to assess conditional eligibility:

- The TWEAK alcohol screening test will be administered. A score of < 4 is required for study eligibility.
- Records of at least two previous attacks (including laboratory results and/or imaging studies) must be obtained and reviewed to determine if the attacks meet inclusion criteria.
- Films from a clinically indicated MRCP procedure must be reviewed with a radiologist at the recruiting site to confirm pancreas divisum, rule out definitive changes of calcific chronic pancreatitis, and to rule out other etiologies of acute pancreatitis. The MRCP procedure is performed as part of standard of care and will not be performed specifically for research purposes.
- Study personnel will interview the subject and review medical records to confirm remaining eligibility criteria.

Pre-Randomization Screening Procedures:

Additional procedures required to determine eligibility must be performed immediately prior to and during EUS at the Randomization/Treatment visit.

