- 2) Amylase or lipase $\geq 3x$ the upper limit of normal at least 24 hours after the procedure, and
- 3) Hospitalization (or prolongation of existing hospitalization) for at least 2 days.

The diagnosis of post-ERCP pancreatitis will be made based on review of medical records including clinical notes, results of lab tests and imaging studies.

Subjects who develop post-ERCP pancreatitis will be managed per standard clinical practice by the unblinded physician investigator. After recovery, subjects will continue to be followed per study protocol.

9.4.2 18 Month Follow-up

At approximately 18 months post-randomization, subjects will undergo an MRI with intravenous contrast (gadolinium) and MRCP protocol with secretin (a pancreatic secretagogue) enhancement if available to assess for interval morphological and/or functional changes of chronic pancreatitis. Gadolinium may be withheld if the glomerular filtration rate is < 30 mL/minute) or allergy. If there is a contraindication to MRI, a pancreas protocol contrast-enhanced computed tomography (CECT) scan will be performed. These images will be interpreted locally; de-identified images will be stored on a central radiology server at MUSC for future ancillary studies. Each site will have their own methods for removing personal health identifiers including metadata, before submitting the films to the Statistical and Data Coordinating Center for storage. If an MRI/MRCP had been performed within 6 months of these study time points, and is considered to be of adequate quality, then a repeat scan will be deferred. Images of MRI/MRCP scans, if performed at other intervals during the follow-up period, and available, will also be sent to a central radiology

server. If the subject is pregnant at the 18-month encounter, the MRI will not be performed until post-partum.

If the subject has not already been diagnosed with diabetes mellitus, assessment for diabetes mellitus will be performed at the 18-month follow-up encounter (fasting or random blood glucose and hemoglobin A1c). If the subject has not been diagnosed with exocrine insufficiency, subjects will undergo fecal elastase testing at the 18-month follow-up encounter.

9.4.3 Telephone follow-up (6 months, 12 months, 24 months, 30 months, 36 months, 42 months, 48 months)

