12.4 Exploratory Aim #4. Progression to chronic pancreatitis.

Interval development of chronic pancreatitis will be defined as the development of morphological changes of chronic pancreatitis during follow-up; specifically, the interval development of parenchymal or ductal calcifications or main pancreatic duct stricture. These will be measured by radiographic interpretation of study MRI scans at month 18, or through other radiological imaging obtained during clinical care.

Interval development of new-onset diabetes mellitus will be confirmed when a patient has abnormal values on two of the following tests or two abnormal values of the same test: a) Fasting blood sugar ≥ 126 mg/dl; b) HbA1c $\geq 6.5\%$; c) Random blood sugar ≥ 200 mg/dl measured at month 18, or laboratory testing through routine clinical care, or are receiving antidiabetic medication(s) for treatment of diabetes mellitus.

Interval development of exocrine pancreatic insufficiency will be defined using the fecal elastase test measured at month 18 (or laboratory testing through routine clinical care), defined as one fecal elastase concentration <100 mcg/g stool or two values between 100-200 mcg/g stool.

12.5 Exploratory Aim #5. Biorepository.

The goal of biospecimen procurement (exploratory specific aim #4) is to establish a biorepository for future translational studies. These studies would explore risk factors for recurrent acute pancreatitis, progression to chronic pancreatitis and its sequelae, and factors associated with response to miES. We will collect blood and urine from subjects in both the randomized and observational cohorts who consent to participation in the biorepository. All samples will be labeled with the SHARP study ID and no personal health identifiers. Samples collected at participating centers will be shipped to the University of Pittsburgh central biorepository and stored at this facility throughout the study period. Following the SHARP trial, remaining samples will be shipped to a designated NIDDK Biosample Repository.

All samples and data transferred to the Pittsburgh Repository will be under the custodianship of the SHARP PIs, although the study's Steering Committee will have proprietary control of and exclusive access to the samples and data for an agreed-upon period of time. Subsequently, samples and data will be available to the wider

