15. STATISTICAL CONSIDERATIONS

15.1 Sample Size and Power Estimation

Since the natural history of iRAP is poorly understood, risk estimates are based on previous small clinical trials and epidemiological studies. Based on a previous small trial of ERCP for RAP in pancreas divisum with limited (1-year) follow-up for the majority of patients, the probability of developing a third episode of AP is 70%.(Lans, Geenen et al. 1992) Natural history studies specific to divisum are lacking, but retrospective cohort studies and one surgical series suggest the recurrence rate following minor papilla stenting, miES, or surgical sphincteroplasty are 15-50%(Attwell, Borak et al. 2006, Chacko, Chen et al. 2008, Borak, Romagnuolo et al. 2009, Crino, Bernardoni et al. 2017). Given the short-term risk of post-ERCP pancreatitis (~10%), costs of ERCP, and potential for post-sphincterotomy re-stenosis, we believe a minimum effect size of 33% (relative risk reduction) is of clinical relevance. This effect size was agreed upon by the site principal investigators as the least clinically significant benefit for ERCP, considering the risks of ERCP and available data on this topic. Since AP recurrence is variable and time sensitive, we propose a reduction in risk of subsequent acute pancreatitis during follow-up as the primary outcome, defined by the median time to acute pancreatitis recurrence (a time-to-event measure). We assume the risk of recurrence within 12 months of randomization is 60% in EUS + sham and 40% in EUS + ERCP with miES groups, with the median time to recurrence being 9.1 and 16.3 months for EUS + sham and EUS + ERCP with miES groups, respectively. Assuming an exponential hazard, a 2-sided alpha error of 5%, power 85%, and non-adherence of 20% (this includes technical crossovers when sphincterotomy cannot be performed and competing events/risks), the trial requires a total sample size of approximately 234 (n=117 per group).

We recognize that sample size estimation is based on assumptions and if the event rate is lower than assumed, we may begin to see a decrease in power. To reduce the likelihood of an underpowered study due to incorrect assumptions, a sample size re-estimation will be conducted during the enrollment period. Details of this plan as well as all statistical considerations are outlined in the SHARP Statistical Analysis Plan.

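### Aim 4 counts chronic pancreatitis found on any clinical-care scan, so detection can differ modestly by arm even when true progression is equal

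*Combined protocol and SAP*

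**What the plan says.** Section 12.4 sets the case definition for Aim 4. New parenchymal or ductal calcification, or a new main-duct stricture, counts as interval chronic pancreatitis, and "These will be measured by radiographic interpretation of study MRI scans at month 18, or through other radiological imaging obtained during clinical care". No limit is placed on the modality, timing or reason for a clinical scan, and the section does not name the examination against which change is judged.

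Other sections bear on this:
- Section 4.4 calls Aim 4 exploratory, expects few transitions, and offers the month-18 scan only to patients enrolled early enough to reach it.
- Section 9.4.2 has scans read locally. The study scan is waived under this condition: "If an MRI/MRCP had been performed within 6 months of these study time points, and is considered to be of adequate quality".
- Section 9.4.4 lists radiology among the evaluations a blinded site investigator may order for a suspected attack. Section 12.1 makes imaging one of the three diagnostic criteria, naming CECT first.
- Of the entry MRCP, section 8.2 says: "The MRCP procedure is performed as part of standard of care and will not be performed specifically for research purposes". No age limit is given for it.
- Section 6.2 excludes "Calcific chronic pancreatitis, defined as parenchymal or ductal calcifications identified on computed tomography or magnetic resonance imaging scan". Its footnote requires EUS to confirm the absence of stricture before randomization, and section 9.2 has parenchymal and ductal changes recorded on a standardized EUS form at that visit.

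**The concern.** A lesion can be counted only if someone looks for it. The month-18 scan is scheduled alike in both arms, but clinical scans follow symptoms. If miES reduces attacks as hypothesized, sham patients will have more clinical scans and more chances to be called a case. Under uniform accrual, more than a quarter of patients will not reach month 18 before database lock, and for them clinical imaging is the only route to becoming a case. Blinding of patients and assessors does not help, because allocation acts through the attacks themselves.

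Since few true transitions are expected, a handful of extra detections in one arm could be read as slower disease progression in the other.

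**Working it through.** **1. Attack rates and the plan's own figure.** Section 15.1 assumes "the risk of recurrence within 12 months of randomization is 60% in EUS + sham and 40% in EUS + ERCP with miES groups". Exponential monthly hazards are −ln(0.4)/12 = 0.0764 for sham and −ln(0.6)/12 = 0.0426 for miES, a hazard ratio of 0.557. The medians are ln 2/0.0764 = 9.1 and ln 2/0.0426 = 16.3 months, matching the plan.

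Schoenfeld's formula (two-sided 5%, power 85%) needs 106 events. Follow-up taken as uniform from 6 to 48 months (section 5.4) gives event probabilities of 0.811 and 0.639, mean 0.725. Then 106/0.725 = 146.2, and 146.2/(1 − 0.20)² = 228.4. Taking one month off follow-up for the 30-day window gives 149.4/0.64 = 233.4, or 234 as stated. The plan does not give its inflation method; this is one route that reaches its figure, so the rates are usable as inputs.

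**2. Scan exposure.** Mean follow-up is (6 + 48)/2 = 27 months. If the first-recurrence hazard continues as a constant attack rate (assumption), expected attacks are 27 × 0.0764 = 2.06 for sham and 27 × 0.0426 = 1.15 for miES. If a share p of attacks is scanned, the proportion with at least one clinical scan is 1 − [exp(−6pλ) − exp(−48pλ)]/(42pλ), where λ is the monthly hazard:
- p = 25%: 39% vs 24%
- p = 50%: 60% vs 42%
- p = 75%: 73% vs 55%

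The share not reaching month 18 is (18 − 6)/(48 − 6) = 12/42 = 29%.

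**3. Apparent progression with identical true progression.** Simulation of 2 million patients per arm, with Poisson attacks at these rates. The denominator is all randomized patients. True progression is 5% per year unless noted. Reads are perfect and month-18 attendance is 100% unless noted. The documents give none of these inputs. The last column is the rejection rate of a two-sided 5% test with 117 per arm.

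| Rule and assumptions | Sham | miES | Ratio | Rejection |
|---|---|---|---|---|
| Month 18 only | 5.3% | 5.3% | 1.00 | 5.0% |
| Month 18 only; sensitivity 80%, 2% false positives, 90% attendance | 5.0% | 5.0% | 1.00 | 5.0% |
| Any scan, 25% of attacks scanned | 6.1% | 5.8% | 1.06 | 5.1% |
| Any scan, 50% | 6.8% | 6.3% | 1.08 | 5.3% |
| Any scan, 75% | 7.3% | 6.6% | 1.11 | 5.5% |
| Any scan, 50%, 2% per year | 2.7% | 2.5% | 1.09 | 5.1% |
| Any scan, 50%, 10% per year | 13.3% | 12.2% | 1.09 | 5.7% |
| Any scan, 50%; 2% false positives only | 9.9% | 8.5% | 1.16 | 6.5% |
| Any scan, 50%; sensitivity 80%, 2% false positives, 90% attendance | 8.8% | 7.3% | 1.22 | 7.3% |
| As above, plus 5% with lesions missed at baseline | 12.0% | 10.2% | 1.18 | 7.2% |
| Any scan, 75%; sensitivity 80%, 5% false positives, 80% attendance, 5% missed at baseline | 18.4% | 14.4% | 1.28 | 13.0% |

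The first row checks by hand: (1 − 0.95^1.5) × 30/42 = 0.074 × 0.714 = 5.3%. In patients, the perfect-read case with half of attacks scanned is a gap of 0.005 × 117 = 0.6 per arm; the most adverse row is 0.040 × 117 = 4.7.

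**4. Direction.** In step 3, with half of attacks scanned, the mean number of clinical scans is 1.03 for sham and 0.57 for miES, a gap of about 0.46. Section 11 puts post-ERCP pancreatitis at 10-20%. If half of those were scanned (assumption, not in the simulation), miES gains 0.05 to 0.10 scans per patient. That is smaller than the gap if miES works as planned. If miES barely changes attacks, it is the larger force and points the other way.

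**The case against.** Much can fairly be said for the plan. Both arms have the scheduled scan, which is why the distortion is small when reads are correct. Aim 4 is exploratory; section 4.4 speaks of quantifying progression during clinical care, so capturing clinical scans is deliberate. Section 15.3 leaves the analysis to the SAP, whose text is not in the document reviewed and which may already restrict the comparison. The attack counts extend a first-event hazard to repeat attacks. They ignore the plan's 20% non-adherence and the follow-up ERCPs permitted by section 9.6, both of which could narrow the gap. All this limits the size; none of it changes the rule in 12.4.

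Four stronger readings are not supported:
- *The baseline is undated.* Stricture has a dated check, EUS at randomization. The missing age limit on the MRCP matters mainly for calcification, and by itself it affects both arms equally.
- *Attack scans routinely replace the study scan.* Only an MRI/MRCP of adequate quality can. A CECT cannot, and MRI is described as less common in diagnosing attacks. Attack risk is therefore not a substitution rate.
- *A large pool of CT-visible calcification enters unseen, so apparent progression follows scan exposure (0.60/0.42, about 1.4).* Every patient has had at least two attacks, with records reviewed, and calcification on CT excludes. If CT is common in attacks, few such patients should remain at entry. That ratio also needs the month-18 MRI to miss what CT shows, on which the documents give no figure.
- *Aim 4 will show a false benefit of miES.* The direction is not assured, as step 4 shows.

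**Conclusion.** The point holds in a limited form. As written, section 12.4 lets attack-driven imaging create cases, so detection can depend on arm when progression does not. With equal true progression the apparent ratio is about 1.06 to 1.11 with perfect reads. It is about 1.2 to 1.3 (1.16 to 1.28 in the runs shown) once false-positive local reads are allowed, with or without imperfect sensitivity and missed baseline lesions. The excess is probably on sham.

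These figures rest on the plan's attack rates treated as constant and on assumed progression, scanning share, read accuracy and attendance. They also assume that CT and MRI detect lesions equally well. Severity is minor: the aim is exploratory and the primary analysis is unaffected.

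**What to change.** In section 12.4:
- Base any between-arm comparison of morphological progression on the scheduled month-18 scan (MRI/MRCP, or the protocol's CECT where MRI is contraindicated), among patients whose enrollment date allows it. Enrollment date is fixed before allocation, so this restriction does not depend on arm.
- Report findings from clinical-care imaging separately, by arm and scan source, as a supplementary result.
- Treat calcification or stricture already recorded on the entry MRCP or on the standardized EUS form at randomization as prevalent, not interval.

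Section 9.4.2 and the CECT text in section 11 provide a month-18 CECT when MRI is contraindicated, while the MRI paragraph of section 11 says such subjects do not take part in this component. These passages must be reconciled.

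The cost is wording, plus fewer counted cases in the main comparison. It leaves out the roughly 29% who do not reach month 18 and any change after month 18. Both remain in the supplementary result, so no data are discarded.

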13. DATA MANAGEMENT

13.1 Site Monitoring

The Site Monitoring Plan will be guided by the FDA Guidance on Risk-Based Monitoring and will be a combination of remote and on-site monitoring. The Site Monitoring Plan will detail the monitoring plan and will be part of the MOP. Briefly, the designated monitor(s) will be able to check regulatory documents and certain CRFs remotely and the DCU will work with each site to develop the best plan (i.e., remote access to medical records). In addition to remote monitoring, the monitor(s) will visit the Clinical Centers at specified intervals for the purposes of comparing source documents (such as hospital/clinical charts) to electronic Case Report Forms (CRFs) and database verification. This review will also verify adherence to local regulations for conducting clinical research, protocol eligibility criteria and protocol schedule, and to ensure the consistency, accuracy, and completeness of the data. During both remote and on-site monitoring, the monitor will ensure that subject confidentiality is maintained and that PHI is protected. The investigator agrees that he/she will ensure that any issues, problems, or need for corrections that arise during the conduct of the study will be resolved in a timely manner.

13.2 Remote Monitoring of Informed Consent

In an effort to review informed consent forms in a timely manner, enrolling sites will upload a pdf of the signed informed consent form, into the password protected clinical trial management system, WebDCU™. The PDF file will be linked to the subject ID but will be stored on a secure server separate from the study's CRF data. The secure server on which these files are stored is not backed up to prevent copies of files containing Individually identifiable health information from being copied and stored on non-SDCC back up servers. The files on these servers can only be accessed by designated study personnel upon entry of a second password. SDCC staff will remotely monitor the informed consent forms and issues identified will be relayed to the clinical site for corrective and preventative action. After remote monitoring is complete, the PDF file containing the informed consent form will be permanently deleted from the secure server. If a subject must be re-consented, the process will repeat itself.

13.3 Data Management

Data management will be handled by the Data Coordination Unit (DCU) in the Department of Public Health Sciences at the Medical University of South Carolina (MUSC). All study activities will be conducted in coordination with the study PIs, the clinical sites, and NIDDK, and will use an electronic data acquisition method where all study specific clinical data will be entered by the site personnel in real time. The latest version of each CRF will be available as a PDF file on the study website for use as worksheets and source documents by study personnel.

The study data will be managed (including data queries) by the DCU using the WebDCU™ system. This user-friendly web-based database system, developed by the DCU, will be used for regulatory document management, subject enrollment/randomization, data entry, data validation, project progress monitoring, subject tracking, site monitoring, user customizable report generation and secure data transfer. Upon entry of CRFs into the study database, quality control procedures will be applied at each stage of data handling in order to ensure compliance with GCP guidelines, integrity of the study data, and document processing system reliability. All sites will be monitored by the DCU and site monitors will conduct periodic site visits to review source documents and case report form information. A quality assurance record audit will be implemented. Audit findings will be used to identify and correct problems.

